4.1 Inclusion Criteria

1. Patients above the age of 18 years old.
2. Patients with a diagnosis of COVID-19 on mechanical ventilation.
3. Patient maximum baseline temperature (within previous 12 hours) < 38.3°C.

4. Patients must have a surrogate or legally authorized representative able to understand and critically review the informed consent form.

4.2 Exclusion Criteria

1. Patients without surrogate or legally authorized representative able to provide informed consent.
2. Patients with contraindication to core warming using an esophageal core warming device.
3. Patients known to be pregnant.
4. Patients with <40 kg of body mass.
5. Patients with DNR status.
6. Patients with acute stroke, post-cardiac arrest, or multiple sclerosis.

4.3 Subject Recruitment

Subjects will be recruited from the ICU or other clinical environment in which they are being treated (Emergency Department, step-down unit, etc.). Patients will be identified by the PI or other study investigators/coordinators as available. All patients without a DNR order with a diagnosis of COVID-19 and meeting inclusion criteria will be eligible for screening for any exclusion criteria. The study team will pre-screen the potential subject's EMR, to assess all other inclusion/exclusion criteria, prior to approaching the patient and/or their surrogate / legally authorized representative about study participation. Written informed consent for the research study will be obtained from patient's surrogate or legally authorized representative prior to enrollment. If a patient enrolled in the study gains the capacity to consent for him/herself while the study is in progress, the patient will be approached by a study team member and the consent document will be presented directly to the patient. All questions the patient might have will be answered. The patient will be given the opportunity to either withdraw from the study or sign the consent form. The patient will be informed that his or her decision to withdraw from the study will not affect his or her medical care

4.4 Duration of Study Participation

Participants will be involved for approximately 30 days, including screening, treatment, and follow-up. After consent, patient participation in the intervention phase will last 72 hours for active treatment. The follow up for determination of outcome and duration of mechanical ventilation will occur at 1-month post-treatment. Additional data will be collected via chart review.

4.5 Total Number of Subjects and Sites

Recruitment will end when 22 participants are randomized.

5 Study Intervention

5.1 Intervention Regimen

Patients who are randomized to core warming will have the esophageal heat transfer device placed in the ICU or other treatment area where patient is undergoing mechanical ventilation. The device will remain in place until the study is completed (72 hours). The device will be set to 42°C for the duration of the study period, with the exception of any elevations in patient temperature as described in section 3 above.

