1.3 Name and Description of the Core Warming Device

Core warming will be performed using an esophageal heat transfer device (ensoETM, Attune Medical, Chicago, IL) This device is an FDA cleared device, and is a multi-lumen silicone tube placed in the esophagus for the purpose of cooling or warming a patient while simultaneously allowing gastric decompression and drainage. Modulation and control of the patient's temperature is achieved by connecting the device to an external heat exchanger. Two lumens connect to the external heat exchanger, while a third central lumen provides stomach access for connection to a fluid collection device with low intermittent suction for gastric decompression. Distilled water circulates within the device just like a water blanket. The device can be placed by most providers in the operating room, emergency room, or intensive care unit. It is a single-use, disposable, non-implantable device with an intended duration of use of 72 hours or less. For this study, the device will be used during mechanical ventilation of patients with diagnosed COVID-19, under the intended indication of patient temperature management as detailed in the product instructions for use.

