6.3 Rescue Therapy

The core warming device will be removed and replaced if at any time there is evidence of a potential device malfunction. The device can be easily removed and replaced during treatment if needed. Should evidence of continued malfunction occur after replacement of the study device, the device will be removed, allowing the patient to undergo the standard of care with respect to temperature monitoring and control.

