6.5 Subject Withdrawal

Subjects may withdraw from the study at any time without impact to their care. They may also be discontinued from the study at the discretion of the Investigator for lack of adherence to study procedures or visit schedules, AEs, or should it become clinically necessary to deviate from the study protocol during the course of the study. The Investigator may also withdraw subjects who violate the study plan, or to protect the subject for reasons of safety or for administrative reasons. It will be documented whether or not each subject completes the clinical study. We will attempt to have one final visit or contact to follow up regarding adverse events for participants who withdraw prior to the 30 day follow up visit.

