7.4 Subject Population(s) for Analysis

All patients enrolled, randomized to a study arm, and completed in the study will be included for analysis.

8 Safety and Adverse Events

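### Section 7.4 analyses only randomised patients who completed, never defines completion, and so lets post-randomisation events and unblinded discretion decide who is compared

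*Combined protocol and SAP*

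**What the plan says.** **Analysis population.** Section 7.4 reads: "All patients enrolled, randomized to a study arm, and completed in the study will be included for analysis". No other population is defined for the efficacy endpoints, and no section contains an intention-to-treat statement. Section 7.3.2 separately says that adverse-event information will be gathered on every randomised patient for the safety analysis.

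**Completion.** Section 6.5 promises a record of it ("It will be documented whether or not each subject completes the clinical study") but gives no criterion.

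**Discontinuation.** Section 6.5 says of patients: "They may also be discontinued from the study at the discretion of the Investigator for lack of adherence to study procedures or visit schedules". The same sentence adds adverse events and departures from protocol that care makes necessary. A later sentence adds safety and administrative reasons. Under 5.2 and 8.6, physicians and study team know the assignment.

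**Time on the device.** Section 5.1 says: "The device will remain in place until the study is completed (72 hours". Its only stated exception concerns the temperature setting. Section 4.4 agrees: "patient participation in the intervention phase will last 72 hours for active treatment". Section 1.3 is looser: "the device will be used during mechanical ventilation of patients with diagnosed COVID-19", with an "intended duration of use of 72 hours or less". Section 6.3 covers repeated malfunction: "the device will be removed, allowing the patient to undergo the standard of care". It does not say that the patient then leaves the study. No section says what happens when a patient is extubated before 72 hours.

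**The concern.** Randomisation makes the two arms comparable at the moment of assignment. A filter applied afterwards keeps them comparable only if it removes patients for reasons unrelated to arm and outcome. Completion is not such a reason in ventilated COVID-19 patients: withdrawal, discontinuation, death and early recovery may all be related to outcome, and some may be related to the device.

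Here the filter is also undefined, and part of the decision lies with staff who know the arm. Whoever prepares the dataset will have to decide what *completed* means, possibly after seeing the outcomes. With 22 patients, one or two such decisions could visibly change a comparison. The plan intends the data to inform larger studies (7.2), so an error would carry forward.

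**Working it through.** The plan gives no power calculation, alpha, effect size or expected attrition (7.2), so there is no figure of its own to reproduce. The check is mainly a comparison of sections.

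**Step 1. What could *completed* mean?**
- *About 72 hours.* Section 5.1 puts 72 hours beside completion of the study. Section 3.1.2 calls 72 hours the study period. Section 6.2.3 places the 30-day review after study completion, so completion must come earlier.
- *Day 30.* Section 6.5.1 treats withdrawal as something that can happen up to the 30-day visit. Section 8.2 runs the study period from consent to Day 30. Section 4.4 gives participation as about 30 days.
- *72 hours of device use.* No section says this. It can be reached only by reading 5.1 as a rule about who completes rather than about when the device comes out.

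**Step 2. Who is analysed under each reading?**
- *72 hours elapsed.* Withdrawals and discontinuations before 72 hours are lost from both arms, and possibly deaths before 72 hours. A patient extubated early stays in unless discontinued.
- *Day 30.* Withdrawals and discontinuations at any time to Day 30 are lost from both arms. If death also counted as non-completion, every patient dead by Day 30 would be removed and the mortality comparison would be empty. That is unlikely to be intended, since mortality is a secondary endpoint (3.2.2), but the text does not rule it out.
- *72 hours of device use.* Group A patients whose device comes out early, through extubation or malfunction, are lost. Group B has no counterpart.

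**Step 3. The extubation example.** A Group A patient is extubated at, say, 48 hours and the device is removed. Section 1.3 is consistent with this; 5.1 and 4.4, read literally, are not. Section 6.5 permits discontinuation but does not require it, and 6.3 shows a removal with none mentioned. The plan does not settle whether this patient is analysed.

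**Step 4. Arithmetic.** One patient is 1/11 = 9.1% of an arm (11 per arm, section 3.1). The share p extubated before 72 hours is not in the documents; 5%, 10% and 20% are assumptions. The chance of at least one such patient in Group A is 1 − (1 − p)^11:
- p = 0.05: 1 − 0.95^11 = 0.431
- p = 0.10: 1 − 0.90^11 = 0.686
- p = 0.20: 1 − 0.80^11 = 0.914

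The expected number is 11p = 0.55, 1.10 and 2.20. These figures count patients for whom the question would arise, not patients excluded.

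**Step 5. Illustration only, under the least supported reading.** Suppose warming has no effect, ventilation duration T is lognormal with log-SD 0.6 or 0.8, the median is set so that P(T < 3 d) = p, and only Group A patients with T < 3 d are dropped. The shift in the Group A mean is E[T | T ≥ 3] − E[T]. For log-SD 0.6 and p = 0.05: median 3·exp(0.6 × 1.645) = 8.05 d; mean 8.05·exp(0.18) = 9.64 d; ratio Φ(0.6 + 1.645)/0.95 = 0.9876/0.95 = 1.0396; shift 9.64 × 0.0396 = 0.38 d. Over all settings the shift is 0.38 to 1.52 d, against warming. In simulation (11 per arm, 8,000 trials per setting, two-sided Mann–Whitney at an assumed 0.05), rejection is 4.8–9.6%, compared with 4.6–4.9% when all are kept. It is clearly above 5% only near p = 0.20. If such patients are dropped from both arms the expected difference is zero; if nobody is dropped the bias is zero.

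This model has no deaths and starts the ventilation clock at device placement. Section 4.1 sets no limit on prior ventilation and no section defines when duration starts, so these figures do not estimate this trial's bias.

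**The case against.** A reader might infer that early-extubated Group A patients will be dropped and that the trial is therefore biased against warming by a known amount. The documents do not support that. Sections 7.4 and 6.5 speak of completing the study, not of hours on the device. The one described early removal without replacement (6.3) sends the patient to standard care with no discontinuation mentioned. Section 1.3 already implies that use ends with ventilation. On the 72-hours-elapsed or Day-30 reading, an early-extubated patient who is not discontinued is kept.

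Nor can one assume that patients extubated within 72 hours of device placement have the shortest ventilation times. A patient already ventilated for many days at enrolment could have a long total, and early deaths can also give short ones.

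A reader might also fear a false claim of benefit. The extubation example points the other way. Losing deaths or withdrawals could push a comparison in either direction.

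Finally, this is a small pilot without a power calculation, and a sensible team might analyse everyone anyway.

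All of this limits the extubation example and its figures. It does not answer the point about 7.4: the written rule conditions on an undefined post-randomisation status, and good bedside practice does not say who enters the analysis.

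**Conclusion.** The concern holds as a defect in the definition of the analysis population. As written, 7.4 allows randomised patients in either arm to be removed from every efficacy comparison for reasons arising after randomisation, on an undefined criterion and partly at the discretion of unblinded staff. The adverse-event analysis is less exposed, because 7.3.2 refers to all randomised patients.

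Early extubation in Group A is a possible arm-specific route, not a demonstrated one. Neither the number of exclusions nor the resulting bias can be derived from the documents. The day shifts and rejection rates above rest on assumed inputs and should not be quoted as findings. What is firm is the unit of loss, 9.1% of an arm per patient, and that the text permits the loss. For a 22-patient pilot this is a low-cost improvement rather than a fatal flaw.

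**What to change.** **Main change, section 7.4.** Make the primary analysis all randomised patients in their assigned arm, whatever their completion status or time on the device, using all data collected to Day 30 subject to consent. Define *completed* and keep any completer or per-protocol analysis as a labelled sensitivity analysis. Much of what is needed is already provided for: 6.5.1 seeks permission to check survival after withdrawal, and 9.1 keeps data obtained before authorisation is revoked.

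**Supporting clarification, section 5.1.** State that the device stays in for 72 hours or until extubation, whichever is earlier, and that removal at extubation is not a discontinuation under 6.5.

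**Cost.** A few sentences, with no extra patients, tests or endpoints. The downside is some dilution, because patients with less than 72 hours of warming count fully in Group A. Reporting hours on the device by patient makes that visible and needs a recorded removal time. Keeping everyone in the population does not supply PaO₂/FiO₂ values that were never measured after extubation or death, so the plan should also say how those are handled.

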5.2 Blinding

Due to the nature of this study, the physicians will not be blinded to the randomization assignment, however participants will be blinded. Once a subject is randomized, the research team will receive the randomization assignment (core warming or standard of care) and proceed with the procedures per the assignment.

5.3 Device Accountability

Core warming device accountability logs will be kept on file, will be completed on a regular basis, and will include product number, date of use, participant ID code, device damaged/destroyed and date of damage/destruction (including return date if applicable).

6 Schedule of Procedures and Data Extraction

Study Phase	Screening	Randomization/ Intervention Phase		Follow up
Study Days	Day -1to 0	Day 0	Day 1-2	Day 30
Informed Consent	X			
Review Inclusion/Exclusion Criteria	X			
Demographics	X			
Medical History/Interim History*	X			X
Physical Examination*	X		X	X
Vital Signs: Temperature, BP, HR, RR*	X	X	X	X
Height and Weight	X			
Pregnancy Test	X			
Clinical Labs	X	X	X	
Respiratory tract viral load		X	X	
Ventilator settings	X	X	X	
SOFA score	X	X	X	
Clinical Imaging (per routine)	X	X	X	
Prior/Concomitant Medications	X			X
Randomization		X		
Temperature monitoring		X	X	
PaO ₂ , FiO ₂ , parameter recording		X	X	
Adverse Event / Unanticipated Problems Assessment		X	X	X

* Interim medical history, physical exam, and vitals will be collected via chart review from routine clinical care.

6.1 Pre-Screening

Patients will be screened within 24 hours prior to the Baseline/Randomization timepoint to determine potential eligibility.

6.2 Study Visits & Data Collection

6.2.1 Screening, Enrollment, and Randomization

Study personnel will assess each subject against each inclusion and each exclusion criterion and the Investigator will determine the subject's eligibility for study participation. The principal

investigator or documented members of the research team will discuss the underlying rationale for the study, the procedures to be followed, the potential benefits and risks, and other issues mandated by the consent process with the surrogate or legally authorized representative. The participant's surrogate or legally authorized representative will be asked if they would like to participate, and if so, this will be documented using the study ICF. Determining the eligibility for each participant will require information generated during the course of routine clinical care as dictated by their attending physicians. Selected testing data will be collected in order to characterize the type, cause and severity of the patient's need for mechanical ventilation and the treatments received prior to enrollment. The data will include information from the evaluations listed below.

Once the Investigator has reviewed and signed the eligibility checklist, the research staff will enter the participant's information into the RedCap system to obtain the randomization assignment.

Data collection:

- Inclusion/Exclusion criteria review
- Study Informed Consent
- Collect Demographics (including sex/gender, race, ethnicity, and age via date of birth)
- Medical Record Review (including any history of disease, social history, physical exam findings and physicians notes)
- Review of Concurrent Medications
- Physical Exam
- Vital Signs: temperature, blood pressure, heart rate, respiration rate, height and weight
- Routine Clinical Labs/Phlebotomy such as a complete blood count (CBC) and chemistry profiles, along with most recent arterial blood gas for determination of PaO₂, if collected as routine care.
- Specific labs recorded include: sodium, potassium, creatinine, hematocrit, white blood cell count, and CRP, if collected as routine care.
- Lower respiratory tract (tracheal aspirate, sputum) viral load (cycle threshold)
- SOFA score
- Ventilator settings
- Pregnancy test for women of childbearing potential
- Randomization
- Adverse Event/Unanticipated Problem assessment and recording

6.2.2 Post-placement

As part of routine monitoring, participants will have regularly obtained parameters (labs, vital signs, ventilator settings) recorded, as well as viral load at start and end of treatment.

- Interim medical history review
- Physical Exam
- Vital Signs: temperature, blood pressure, heart rate, respiration rate, height and weight

- Routine Clinical Labs/Phlebotomy such as a complete blood count (CBC) and chemistry profiles, along with most recent arterial blood gas for determination of PaO₂, if collected as routine care.
- Specific labs recorded include: sodium, potassium, creatinine, hematocrit, white blood cell count, and CRP, if collected as routine care.
- Lower respiratory tract (tracheal aspirate, sputum) viral load (cycle threshold)
- Ventilator settings
- Adverse Event/Unanticipated Problem assessment and recording

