6.5.1 Data Collection and Follow-up for Withdrawn Subjects

We will attempt to have one final visit or contact to follow up regarding adverse events for participants who withdraw prior to the 30 day follow up visit. During this contact they will be asked for permission to have the study team look into their survival status via their electronic medical records and publicly available means.

7 Statistical Plan

Primary Endpoint

The primary endpoint of this study will be the change in PaO₂/FiO₂ ratio at 0, 24, 48, and 72 hours after implementation of core warming of ventilated patients. This endpoint will be compared between patients receiving core warming and those randomized to undergo standard care (standard temperature management, with or without antipyretics as needed).

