7.3.2 Interim Safety Analysis

All subjects entered into the study and randomized at the baseline timepoint will have detailed information collected on adverse events for the overall study safety analysis. An interim safety analysis will be performed after the first 10 subjects are enrolled in the trial. At this time the safety and tolerability of the study device will be assessed and if deemed safe and appropriate, enrollment will continue to 22 subjects.

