11.1 Risks

Risks of the study procedures are described below:

Core warming risks: Placement of the core warming device, similar to any device in the esophagus, can result in or exacerbate esophageal tissue damage, particularly in patients with known esophageal deformity or evidence of esophageal trauma. These risks are similar to those who receive the standard of care orogastric or nasogastric tubes inserted into the esophagus during routine clinical care of ICU patients.

There is also a risk that placement of the core warming device may result in movement of the tongue to the side, which can persist after removal; however, it is unclear whether this tongue deviation is caused by the endotracheal tube used during mechanical ventilation or if it is part of the disease progression of COVID-19 infection. Tongue deviation is one of the known sequelae of infection with SARS-CoV-2, better known as COVID-19.[53][54][55] Electromyography of the muscles innervated by the pharyngeal, superior laryngeal, and recurrent laryngeal branches of the vagus nerve, and by the accessory and hypoglossal nerves, have shown asymmetric patterns of acute or chronic neurogenic damage, or both.[54] Whether these findings reflect the direct (viral) or indirect (immune-mediated) effect of SARS-CoV-2 remains to be established.[54]

Loss of Confidentiality Risks: There is the potential for loss of confidentiality during data collection.

Temperature modulation risks: Warming critically ill septic patients has been previously investigated, with no unforeseen risks identified. Whole-body hyperthermia (to core body temperatures $> 39.0^{\circ}\text{C}$) has been tested in sedated patients undergoing colorectal surgery, as well as in oncological patients in combination with radiotherapy and/or chemotherapy.[52] Patients in these studies suffered no serious hyperthermia-related side effects despite being warmed to temperatures much higher than targeted in this study.

Potential adverse effects of external warming/body temperature elevation include:

- (1) Vasodilation of arteriovenous shunts in the skin resulting in decreased blood pressure and an increase in vasopressor dose
- (2) Elevated heart rate
- (3) Increased respiratory rate
- (4) Increased metabolic rate
- (5) Patient discomfort
- (6) Sweating
- (7) Worsened long-term neurological function in patients with acute stroke or post-cardiac arrest
- (8) Exacerbation of multiple sclerosis symptoms

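### Vasopressor dose, half of the first-listed warming risk, is not a planned data item during the 72 hours of warming

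*Combined protocol and SAP*

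**What the plan says.** Section 11.1 lists eight potential adverse effects of raising body temperature. The first is "Vasodilation of arteriovenous shunts in the skin resulting in decreased blood pressure and an increase in vasopressor dose".

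The schedule in section 6 has a row "Prior/Concomitant Medications", marked at Screening and Day 30 and blank at Day 0 and Day 1-2. The text agrees: section 6.2.1 (screening) has "Review of Concurrent Medications", section 6.2.3 (post treatment) pairs concomitant medications with the interim history, and section 6.2.2, which covers the warming period, has neither. Section 6.2.2 says that "participants will have regularly obtained parameters (labs, vital signs, ventilator settings) recorded", and its list includes "Vital Signs: temperature, blood pressure, heart rate, respiration rate, height and weight" and adverse event assessment.

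Section 7 (Primary Endpoint) describes control care as "standard temperature management, with or without antipyretics as needed". Section 7.3.2 places an interim safety analysis after the first 10 subjects are enrolled: "At this time the safety and tolerability of the study device will be assessed". Enrolment goes on to 22 if the result is judged acceptable.

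**The concern.** The protocol itself says that this harm would show in two quantities, pressure and vasopressor dose. Only pressure is planned as a recorded variable during exposure. If ICU staff adjust vasopressors to hold a pressure, which is the natural reading of the risk item, the recorded pressure can stay flat while the dose rises. The dose is then the more informative half, and it is the half that is not collected. The protocol's background points the same way: section 1.1 cites a randomized trial of cooling in ventilated septic-shock patients that found a lower vasopressor dose, so the protocol's own evidence treats dose as responsive to temperature.

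At stake is the decision to continue after 10 subjects, and the final safety comparison. Antipyretic use matters for a related reason. It acts on the temperature difference between arms, and without a record by day a small difference is hard to attribute to weak warming, to drugs, or to fever in controls.

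**Working it through.** The plan gives no figure to reproduce on this point. The check is a comparison of sections, plus one calculation on timing.

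**Step 1. What is planned during warming** (section 6 schedule against the section 6.2.2 list)

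| Item | Screening | Day 0 | Day 1-2 | Day 30 | In 6.2.2 list |
|---|---|---|---|---|---|
| Prior/concomitant medications | X | – | – | X | no |
| Vital signs, with blood pressure | X | X | X | X | yes |
| SOFA | X | X | X | – | no |
| Adverse event assessment | – | X | X | X | yes |
| Vasopressor dose | no row | no row | no row | no row | no |
| Antipyretic or cooling use | no row | no row | no row | no row | no |

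Table and text agree on medications, so the blank cells are unlikely to be an artefact of how the table was read. They disagree on SOFA.

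**Step 2. Routes by which the harm can reach the interim review**

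- *Blood pressure.* Recorded during warming, in the schedule row "Vital Signs: Temperature, BP, HR, RR" and in 6.2.2. It shows a fall that is not corrected, but not one corrected by a higher dose.
- *SOFA.* Scheduled on Day 0 and Day 1-2 but missing from 6.2.2. The documents do not list its components or say that it will be tabulated by arm for safety, so it cannot be counted on as a measure of dose.
- *Adverse events.* Recorded from consent to the 30-day follow-up (section 8.2). Section 8.1.1 covers any new or worsening sign, and counts an abnormal diagnostic result if it prompts further treatment. Nothing says that a change in vasopressor dose must be logged. Whether it is logged is a judgement by a team that knows the allocation (sections 5.2 and 8.6) and monitors safety itself (section 8.7).
- *Day 30 medication item.* No look-back period is stated, and Step 3 shows when it becomes available.

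**Step 3. Day 30 medication data on hand when the tenth subject enrols**

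Inputs from the documents: 22 subjects (section 4.5); study duration of about 3 to 5 months (Study Summary); Day 30 counted from the start of treatment (section 3.1.3) or from study completion (section 6.2.3), so d = 30 or 33 days. Assumptions: uniform accrual, 30.4 days per month, follow-up (33 days) either inside or outside the stated duration, and a review held at once.

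With E days of enrolment, the gap between subjects is g = E/22. The tenth enrols at 10g, and subject i has reached the item if i·g + d ≤ 10g, that is, i ≤ 10 − d/g.

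- 3 months including follow-up: E = 91.2 − 33 = 58.2, g = 2.65. For d = 30, 10 − 30/2.65 = −1.3, so **0 of 10**.
- 4 months, all enrolment: E = 121.6, g = 5.53. For d = 30, 10 − 5.42 = 4.58, so **4 of 10**.
- 5 months, all enrolment: E = 152, g = 6.91. For d = 30, 10 − 4.34 = 5.66; for d = 33, 10 − 4.78 = 5.22; so **5 of 10** either way.

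The other combinations fall between these. The item is therefore not yet due for 5 to 10 of the 10 subjects. Under 1:1 allocation, about 10 × 0.5 = 5 of the 10 are expected to be device patients; no blocking is described, so the actual number can differ.

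**The case against.** A reader might infer that this harm cannot be seen at all during warming or at the interim. The documents do not support that. Blood pressure and adverse events are recorded during warming, SOFA is scheduled, and section 7.3.2 rests the safety analysis on detailed adverse event information. A marked fall in pressure, or a vasopressor increase reported as an adverse event, would reach the review.

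A reader might also infer that no medication records will exist for the 72 hours. That is not established either. The Day 30 item sits beside an interim history taken by chart review, and section 4.4 allows further data from the chart. A review at Day 30 could reach back over the warming period, and for explaining a temperature difference in the final analysis that would not be too late. What can be said is that the look-back is unspecified, daily detail is not planned, and vasopressors are not named.

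It is also fair that this is a 22-patient pilot, and that the SOFA mismatch taken alone is a small inconsistency between a list and a table.

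These points narrow the concern without removing it. None of the available routes is a planned record of dose in both arms. The adverse event route depends on unblinded judgement, and under-reporting in one arm could not be detected without a dose record in both.

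**Conclusion.** The point holds in a limited form. Vasopressor dose, half of the first-listed temperature risk, is not a planned data item during the 72 hours of exposure in any of the 22 patients. At the interim it can be inferred only from blood pressure, SOFA or adverse event reports, so the arms cannot be compared directly on vasopressor requirement when continuation is decided. Antipyretic use is likewise unscheduled during the 72 hours, and the Day 30 medication item has no stated look-back.

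The section comparison needs no assumption. The 0-to-5-of-10 range rests on uniform accrual and an immediate review, and a delayed review would have more. That pressure can be held by a higher dose is reasoning from the risk item, not a figure in the plan. The change should be made because it is cheap and bears on a continuation decision. The gap does not invalidate the design.

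**What to change.** These are data-collection changes only, abstracted from the existing medication record:

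- In the section 6 schedule, mark concomitant medications at Day 0 and daily to 72 hours.
- In section 6.2.2, add for both arms: vasopressor agent and dose at 0, 24, 48 and 72 hours, with doses expressed in one common unit for analysis; and antipyretic or active cooling use in each 24-hour period.
- List SOFA in section 6.2.2 to match the schedule.
- State the look-back period of the Day 30 medication item in section 6.2.3.
- In sections 7.3.2 and 8.7, state that change in vasopressor dose will be tabulated by arm at the interim and final safety reviews.

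The cost is a few extra fields per patient per day. No procedure is added and no treatment rule changes.
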